### 1) Hepatic Non-hematological DLT

Any one of the following study treatment-related events will be considered a hepatic DLT:

- Any Grade  $\geq 3$  elevation of aspartate aminotransferase (AST), alanine aminotransferase (ALT), or total bilirubin.
- Grade 2 AST or ALT with symptomatic liver inflammation (eg, right upper quadrant tenderness, jaundice, pruritus).
- AST or ALT  $> 3 \times$  ULN and concurrent total bilirubin  $> 2 \times$  ULN without initial findings of cholestasis (elevated serum alkaline phosphatase [ALP] [eg, findings consistent with Hy's law or FDA definition of potential drug-induced liver injury or potential drug-induced liver injury [p-DILI]). Note that this special category of DLT uses ULN rather than Common Toxicity Criteria (CTC) grade for definition.

### 2) Non-hepatic Non-hematological DLT

Any of the following events will be considered a non-hepatic non-hematological DLT:

- Any Grade 2 drug-related uveitis or eye pain or blurred vision that does not respond to topical therapy and does not improve to Grade 1 severity  $\leq 2$  weeks *or* requires systemic treatment.
- Grade 3 drug-related uveitis, pneumonitis, bronchospasm, neurologic toxicity, hypersensitivity reaction, or myocarditis, of any duration or infusion reaction not returning to baseline in  $< 1$  hour, will require discontinuation.

- Any Grade 3 or greater nondermatologic, nonhepatic nonhematological study treatment-related toxicity will be considered a DLT, with the following specific exceptions:
  - ◆ Grade 3 or Grade 4 electrolyte abnormalities that are not complicated by associated clinical adverse experiences, last less than 72 hours, and either resolve spontaneously or respond to conventional medical intervention
  - ◆ Grade 3 nausea, vomiting, or diarrhea that lasts less than 72 hours, and either resolves spontaneously or responds to conventional medical intervention
  - ◆ Isolated Grade 3 elevation of amylase or lipase not associated with clinical or radiographic evidence of pancreatitis
  - ◆ Isolated Grade 3 fever not associated with hemodynamic compromise (eg, hypotension, clinical or laboratory evidence of impaired end-organ perfusion or with other symptoms of infusion-related reactions that returns to  $\leq$  Grade 1 with standard treatment in  $\leq$  1 hour)
  - ◆ Grade 3 endocrinopathy that is well controlled by hormone replacement
  - ◆ Grade 3 tumor flare (defined as pain, irritation, or rash that localizes to sites of known or suspected tumor)
  - ◆ Grade 3 fatigue for  $\leq$  7 days
  - ◆ Grade 3 infusion reaction that returns to Grade 1 in  $\leq$  1 hour

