### **7.4 Dosage Modification**

#### **7.4.1 Dose-Limiting Toxicities**

For the purpose of guiding dose escalation, DLTs will be defined based on the incidence, intensity, and duration of AEs for which no clear alternative cause is identified. The DLT evaluation period will be 42 days (6 weeks). In the event of dose delays for reasons other than a potential DLT, the DLT evaluation period may be extended to include at least 28 days after the start of the sequential doses in Part 1 or at least 14 days after the start of Cycle 2 Day 1 sequential doses in Part 2. Participants requiring dose delays >7 days may be replaced for the purposes of DLT evaluation

but permitted to remain on study treatment unless permanent discontinuation criteria (Section 8.1) are met.

In all study parts, participants who complete the first cycle and do not have a DLT, have not had clinical evidence of disease progression, and are considered suitable for further treatment may receive up to 1 additional cycle of BMS-986277.

Additionally DLT's as defined below will require permanent discontinuation for all study participants regardless of treatment cycle.

In Parts 1 and 2, participants who discontinue due to a DLT during the DLT evaluation period, will be considered as DLT-evaluable participants. Participants who withdraw from the study during the DLT evaluation period for reasons other than a DLT may be replaced with a new participant at the same dose level. The incidence of DLT(s) during the DLT evaluation period will be used in dose escalation decisions and to define the BLRM-RD. AEs occurring after the DLT period will be considered for the purposes of defining the BLRM-RD upon agreement between the Sponsor, Medical Monitor (or designee), and investigators.

Participants experiencing a DLT will enter the safety follow-up period of the study. DLTs occurring after the 6-week DLT evaluation period for Part 1 will be accounted for in determining the BLRM-RD for the combination part.

A DLT is defined as one of the following and considered by the Investigator to be possibly, probably or definitely related to BMS-986277 and/or nivolumab.

AEs will be graded according to the NCI CTCAE v4.03, as listed below:

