## 7.4.2 Dose Delay Criteria for Study Treatment

Study treatment administration should be delayed for the following:

- Potential DLT, until DLT-relatedness is defined.
- Select AEs and laboratory abnormalities:
  - Grade  $\geq$  1 pneumonitis
  - Grade  $\geq$  2 abnormality in AST, ALT, or total bilirubin
  - Grade  $\geq$  2 abnormality in creatinine
  - Grade  $\geq$  2 diarrhea or colitis
  - Grade  $\geq$  2 neurological AE
  - AE, laboratory abnormality, or concurrent illness that, in the judgment of the investigator, warrants delaying study treatment administration.

- Criteria for participants who are required to permanently discontinue both study treatments are listed in [Section 8.1](#). Participants not meeting guidelines for permanent discontinuation will be permitted to resume therapy based on the criteria specified below in [Section 8.1.1](#). Participants eligible to resume study treatment will resume study treatment at the nominal treatment visit following their last received study treatment dose.

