#### **7.4.5 Management of Drug-related Infusion Reactions**

BMS-986277 has the potential to induce hypersensitivity reactions following administration. There is potential risk of cytokine release exhibited with enadenotucirev coupled with potential immune activation from transgenes. These events will be mitigated by an up to 12 hour post infusion observation, laboratory measurements for cytokine release monitoring, staggered dosing of initial participants in each cohort of monotherapy treatment (Part 1) and combination treatment (Part 2) to have no more than 1 patient at a time dosed, and a starting dose selected that is 100 $\times$  below the enadenotucirev RP2D. Refer to [Appendix 10](#) for the treatment algorithm for BMS-986277-associated infusion reactions.

Since nivolumab contains only human immunoglobulin protein sequences, it is unlikely to be immunogenic and induce infusion or hypersensitivity reactions. However, if such a reaction were to occur, it might manifest with fever, chills, rigors, headache, rash, pruritus, arthralgia, hypotension, hypertension, bronchospasm, or other allergic-like reactions. All Grade 3 or 4 infusion reactions should be reported within 24 hours to the study Medical Monitor (or designee) and reported as an SAE if it meets the criteria. Infusion reactions should be graded according to NCI CTCAE (Version 4.03) guidelines.

Treatment recommendations for nivolumab-associated infusion reactions are provided below and may be modified based on local treatment standards and guidelines, as appropriate:

**For Grade 1 symptoms** (mild reaction; infusion interruption not indicated; intervention not indicated):

- Remain at bedside and monitor participant until recovery from symptoms. The following prophylactic premedications are recommended for future infusions: diphenhydramine 50 mg IV (or equivalent) and/or acetaminophen/paracetamol 325 to 1000 mg at least 30 minutes before additional nivolumab administrations.

[figure not shown]
**For Grade 2 symptoms:** (moderate reaction required therapy or infusion interruption but responds promptly to symptomatic treatment (eg, antihistamines, non-steroidal anti-inflammatory drugs, narcotics, corticosteroids, bronchodilators, IV fluids); prophylactic medications indicated for  $\leq 24$  hours):

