- Stop the study drug infusion, begin an IV infusion of normal saline, and treat the participant with diphenhydramine 50 mg IV (or equivalent) and/or acetaminophen/paracetamol 325 to 1000 mg; remain at bedside and monitor participant until resolution of symptoms. Corticosteroid and/or bronchodilator therapy may also be administered as appropriate. If the infusion is interrupted, then restart the infusion at 50% of the original infusion rate when symptoms resolve; if no further complications ensue after 30 minutes, the rate may be increased to 100% of the original infusion rate. Monitor participant closely. If symptoms recur, then no further study medication will be administered at that visit.
- For future infusions, the following prophylactic premedications are recommended: diphenhydramine 50 mg IV (or equivalent) and/or acetaminophen/paracetamol 325 to 1000 mg should be administered at least 30 minutes before treatment infusions. If necessary, corticosteroids (up to 25 mg of hydrocortisone or equivalent) may be used.

**For Grade 3 or 4 symptoms:** (severe reaction, Grade 3: prolonged [ie, not rapidly responsive to symptomatic medication and/or brief interruption of infusion]; recurrence of symptoms following initial improvement; hospitalization indicated for other clinical sequelae (eg, renal impairment, pulmonary infiltrates). Grade 4: Life threatening; pressor or ventilatory support indicated):

- Immediately discontinue infusion of study drug. Begin an IV infusion of normal saline and treat the participant as follows: Recommend bronchodilators, epinephrine 0.2 to 1 mg of a 1:1000 solution for subcutaneous administration or 0.1 to 0.25 mg of a 1:10,000 solution injected slowly for IV administration, and/or diphenhydramine 50 mg IV (or equivalent) with methylprednisolone 100 mg IV (or equivalent), as needed. Participant should be monitored until the Investigator is comfortable that the symptoms will not recur. Study drug will be permanently discontinued. Investigators should follow their institutional guidelines for the treatment of anaphylaxis. Remain at bedside and monitor participant until recovery of the symptoms.

In case of late-occurring hypersensitivity symptoms (eg, appearance of a localized or generalized pruritus within 1 week after treatment), symptomatic treatment may be given (eg, oral antihistamine or corticosteroids).

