  - Any Grade  $\geq 2$  study treatment-related pneumonitis or interstitial lung disease that does not resolve following dose delay and systemic steroids
  - Any Grade 3 non-skin, study treatment-related AE lasting  $> 7$  days, or recurs, with the following exceptions for uveitis, pneumonitis, bronchospasm, diarrhea, colitis, neurologic toxicity, myocarditis, hypersensitivity reactions, infusion reactions not returning to baseline in  $\leq 1$  hour, endocrinopathies and laboratory abnormalities:
    - Grade 3 drug-related uveitis, pneumonitis, bronchospasm, neurologic toxicity, myocarditis, hypersensitivity reaction of any duration, or infusion reaction not returning to baseline in  $\leq 1$  hour requires discontinuation
    - Grade 3 study treatment-related endocrinopathies adequately controlled with only physiologic hormone replacement do not require discontinuation. Adrenal insufficiency requires discontinuation regardless of control with hormone replacement.
    - Grade 3 drug-related laboratory abnormalities do not require treatment discontinuation except:
      - ◆ Grade 3 drug-related thrombocytopenia  $> 7$  days or associated with bleeding requires discontinuation
      - ◆ Grade  $\geq 3$  drug-related AST, ALT or Total Bilirubin requires discontinuation\*
      - ◆ Concurrent AST or ALT  $> 3 \times$  ULN and total bilirubin  $> 2 \times$  ULN
- \* In most cases of Grade 3 AST or ALT elevation, study treatment will be permanently discontinued. If the investigator determines a possible favorable benefit/risk ratio that warrants continuation of study treatment, a discussion between the investigator and the BMS Medical Monitor/designee must occur.
- Any Grade 4 drug-related AE or laboratory abnormality (including but not limited to creatinine, AST, ALT, or Total Bilirubin), except for the following events which do not require discontinuation:
    - Grade 4 neutropenia  $\leq 5$  days

- Grade 4 lymphopenia or leukopenia or asymptomatic amylase or lipase
- Isolated Grade 4 electrolyte imbalances/abnormalities that are not associated with clinical sequelae and are corrected with supplementation/appropriate management within 72 hours of their onset

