## **COMPLIANCE WITH THE PROTOCOL AND PROTOCOL REVISIONS**

The investigator should not implement any deviation or change to the protocol without prior review and documented approval/favorable opinion of an amendment from the IRB/IEC (and if applicable, also by local health authority) except where necessary to eliminate an immediate hazard(s) to study subjects.

If a deviation or change to a protocol is implemented to eliminate an immediate hazard(s) prior to obtaining relevant approval/favorable opinion(s) the deviation or change will be submitted, as soon as possible to:

- IRB/IEC for
- Regulatory Authority(ies), if applicable by local regulations (per national requirements)

Documentation of approval/favorable opinion signed by the chairperson or designee of the IRB(s)/IEC(s) and if applicable, also by local health authority must be sent to BMS.

If an amendment substantially alters the study design or increases the potential risk to the participant: (1) the consent form must be revised and submitted to the IRB(s)/IEC(s) for review and approval/favorable opinion; (2) the revised form must be used to obtain consent from subjects currently enrolled in the study if they are affected by the amendment; and (3) the new form must be used to obtain consent from new subjects prior to enrollment.

If the revision is done via an administrative letter, investigators must inform their IRB(s)/IEC(s).

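### The infusion-reaction exception in Protocol Section 7.4.1 contradicts the section's own DLT criterion for reactions at Grade 1 but not baseline at one hour

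*Protocol*

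**What the plan says.** Protocol Section 7.4.1, item 2, opens a list in which any one of the events counts as a non-hepatic, non-hematological DLT.

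- **Second bullet.** Among Grade 3 drug-related events it lists those "of any duration or infusion reaction not returning to baseline in" less than 1 hour (printed with a strict less-than sign). The bullet ends by saying that discontinuation is required.
- **Third bullet.** Other Grade 3 or higher related toxicity is a DLT, subject to listed exceptions. The last of these is a "Grade 3 infusion reaction that returns to Grade 1 in" 1 hour or less.

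Section 8.1 sets the stopping rule for the same event. Discontinuation is required for a Grade 3 "hypersensitivity reaction of any duration, or infusion reaction not returning to baseline in" 1 hour or less.

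On the use of the count, Section 7.4.1 states: "The incidence of DLT(s) during the DLT evaluation period will be used in dose escalation decisions and to define the BLRM-RD". DLT incidence is a primary endpoint (Table 4-1). SAP Section 5.1.1 takes DLTs as they are recorded on the case report form.

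**The concern.** The two tests in Section 7.4.1 use different end states: baseline in one, Grade 1 in the other. An investigator who finds the exception line first would record no DLT for a reaction that has settled to Grade 1 but not to baseline. One who finds the second bullet first would record a DLT. The first investigator would then also face Section 8.1, which stops treatment for a reaction just classed as not dose-limiting.

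At stake is consistent coding of the variable to which the BLRM is fitted, in cohorts of three. Infusion reactions are an anticipated toxicity of this agent (Section 7.4.5). The SAP relies on the recorded flag and describes no later re-adjudication.

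**Working it through.** **Step 1. Classify every Grade 3 infusion reaction by its state at one hour.**

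| State | 7.4.1 second bullet | 7.4.1 exception | 8.1 stopping rule |
|---|---|---|---|
| At baseline before 1 hour | not met | exempt | not met |
| At baseline at exactly 1 hour (signs as printed) | DLT | exempt | not met |
| Grade 1, not baseline, at 1 hour | DLT | exempt | discontinue |
| Above Grade 1 at 1 hour | DLT | not exempt | discontinue |

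Only the two middle rows conflict. The third row is the substantive one. The second row depends on a single sign, strict in Section 7.4.1 and inclusive in Section 8.1. That may be a character lost in conversion and should be checked on the printed page.

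**Step 2. Set up the model, to see what one reclassified event does.** From Appendix 9: logit p(d) = log α + β·log(d / 3×10^12), with binomial DLT counts. The prior for (log α, log β) is the mixture row of Table 2: means (−0.959, 0.884), SDs (1.005, 1.240), correlation 0.055. The posterior was computed on a 1201 × 1201 grid over ±7 SD. P(over) is the posterior probability that the DLT rate is 33% or more; the protocol's cap is 35%.

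**Step 3. Reproduce the plan's example** (Figure 2: 0/3 at 3×10^10, 1/3 at 3×10^11).

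| Quantity | Plan | Recomputed |
|---|---|---|
| P(target), 3×10^10 | 0.068 | 0.068 |
| P(target), 3×10^11 | 0.254 | 0.257 |
| P(target), 1×10^12 | 0.418 | 0.415 |
| P(over), 3×10^12 | 0.579 | 0.561 |

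The largest gap is 0.579 − 0.561 = 0.018. Results that close to the cap are not used to infer a decision.

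**Step 4. Add one DLT.** Doses not mentioned as changed have 0/3.

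- *At 1×10^12, 0/3 to 1/3.* Appendix 9, Section 3.1, itself gives escalate for 0/3 and stay for 1/3. The recomputed P(over) at 3×10^12 is 0.348 and then 0.523. The first is too near 0.35 to rely on, so the decision change rests on the protocol's statement.
- *At 3×10^11, 0/3 to 1/3.* The next step does not change: both lead to 1×10^12 (Section 3.1 and the Figure 2 text). The event stays in the model, though. Once 1×10^12 has 0/3, P(over) at 3×10^12 is 0.404 instead of 0.348 (a second run gave 0.407 and 0.351).
- *At 3×10^11, 1/3 to 2/3, before 1×10^12 is dosed.* P(over) at 1×10^12 goes from 0.225 to 0.526, across the cap.
- *At 3×10^12, six treated.* 0/6 to 1/6 moves P(over) from 0.046 to 0.165, both under the cap. 1/6 to 2/6 moves it from 0.165 to 0.385.
- *At 3×10^12, three treated.* 0/3 to 1/3 moves it from 0.128 to 0.368. The excess over the cap, 0.368 − 0.35 = 0.018, equals the reproduction gap, so no conclusion is drawn.

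**Step 5. Frequency.** The documents give none. If a participant has chance q of such a reaction (an assumption), the chance of at least one in a cohort of three is 1 − (1 − q)^3: 5.9%, 14.3%, 27.1% and 48.8% for q = 2%, 5%, 10% and 20%. The nivolumab text in Section 7.4.5 describes Grade 3 reactions as prolonged or recurrent, which points to the low end.

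**The case against.** The strongest reply is that the list already settles the matter. Its events are alternatives, and the exceptions sit under the third bullet and qualify only that bullet. A reaction that meets the second bullet is then a DLT whatever the third exempts, and no precedence clause is needed. The exception keeps some work, since it spares reactions back to baseline within the hour that the third bullet would otherwise catch. Nor does the second bullet's closing remark on discontinuation make it merely a treatment rule, because Section 7.4.1 requires permanent discontinuation for every DLT. This stands as the better reading. It does not cure the exception, which names Grade 1 and so tells the investigator that a reaction the list counts is not a DLT.

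Second, there are controls. Section 7.4.2 delays dosing for a "Potential DLT, until DLT-relatedness is defined". Section 7.4.5 says: "All Grade 3 or 4 infusion reactions should be reported within 24 hours to the study Medical Monitor (or designee"). Clinical assessment of all data sits above the model. These make divergent coding less likely, but whoever adjudicates still has both sentences to apply.

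Third, Appendix 10, which governs reactions to BMS-986277, is not in the public text and might speak to this. That limit is real. The nivolumab guidance for Grade 3 or 4 reactions in Section 7.4.5, "Study drug will be permanently discontinued", governs treatment and does not define a DLT.

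Fourth, the Grade 1 test could be adopted instead, as in the neighbouring fever exception. That would remove the overlap within Section 7.4.1 but leave a non-DLT that Section 8.1 still stops.

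**Conclusion.** The point holds as a minor inconsistency. One class of reaction, at Grade 1 but not baseline at one hour, is a DLT under the better reading of Section 7.4.1 and a stopping event under Section 8.1, while a written exception says it is not a DLT.

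A reader might infer more, and the documents do not support it:

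- *That the DLT definition is undetermined, or that a wrong dose would follow.* The list structure favours one answer, controls exist, few events are expected, and no dosing error is shown.
- *That three incompatible tests are in force.* The third form, and the conflict at exactly one hour, rest on one sign that may not be genuine.
- *That one event always changes the dose.* The effect depends on the dose and on the DLTs already counted. It changes the protocol's stated decision at 1×10^12, but not the immediate next step at 3×10^11 when the count moves from 0/3 to 1/3.

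The recomputed probabilities assume the fitted prior in Table 2 and three per cohort unless six are stated. Confidence is medium, because Appendix 10 could not be read.

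**What to change.** 1. Reword the last exception in Section 7.4.1, item 2, to: *Grade 3 infusion reaction that returns to baseline in ≤ 1 hour*.
2. Give the second bullet the Section 8.1 limit (baseline, one hour inclusive), if the printed strict sign is genuine, and say in the bullet that the event is a DLT.
3. Leave Section 8.1, the fever exception and the nivolumab treatment guidance as they are.
4. Check that Appendix 10 agrees, and re-check the DLT flag of any recorded Grade 3 infusion reaction before the next model update.

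The cost is two phrases, with no change to design, stopping rules or sample size. Appendix 2 states: "The investigator should not implement any deviation or change to the protocol without prior review and documented approval/favorable opinion of an amendment", so the wording needs ethics committee approval and can travel with the next routine amendment. The trade-off runs both ways. A few reactions at Grade 1 but not baseline at one hour will count as DLTs, which is conservative. A reaction back to baseline at exactly one hour will not count, which is slightly less strict than the second bullet as printed.

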### 3) Dermatologic DLT

- Grade 3/4 rash if no improvement (ie, resolution to Grade  $\leq$  1) after a 1-week to 2-week infusion delay. Participants who have not experienced a Grade 3 drug-related skin AE may resume treatment in the presence of Grade 2 skin toxicity.
- Grade 4 rash of any duration

### 4) Hematologic DLT

- Grade 4 neutropenia  $\geq$  5 days in duration
- Grade 4 thrombocytopenia or Grade 3 thrombocytopenia with clinically significant bleeding or any requirement for platelet transfusion
- Grade 4 anemia not explained by underlying disease
- Grade 4 febrile neutropenia
- Grade 3 febrile neutropenia that lasts  $>$  48 hours
- Grade  $\geq$  3 hemolysis (ie, requiring transfusion or medical intervention such as steroids)

## 7.4.2 Dose Delay Criteria for Study Treatment

Study treatment administration should be delayed for the following:

- Potential DLT, until DLT-relatedness is defined.
- Select AEs and laboratory abnormalities:
  - Grade  $\geq$  1 pneumonitis
  - Grade  $\geq$  2 abnormality in AST, ALT, or total bilirubin
  - Grade  $\geq$  2 abnormality in creatinine
  - Grade  $\geq$  2 diarrhea or colitis
  - Grade  $\geq$  2 neurological AE
  - AE, laboratory abnormality, or concurrent illness that, in the judgment of the investigator, warrants delaying study treatment administration.

- Criteria for participants who are required to permanently discontinue both study treatments are listed in [Section 8.1](#). Participants not meeting guidelines for permanent discontinuation will be permitted to resume therapy based on the criteria specified below in [Section 8.1.1](#). Participants eligible to resume study treatment will resume study treatment at the nominal treatment visit following their last received study treatment dose.

